### **1.1.2 Rationale for conducting this study**

The treatment options for patients who remain uncontrolled by ICS-LABA are extremely limited. In previous clinical studies, benralizumab administration resulted in rapid and prolonged depletion of eosinophils in the peripheral blood and in the asthmatic airway with associated improvements in multiple metrics of asthma control. The magnitude of clinical improvement was positively correlated with baseline blood eosinophil counts and was most consistently observed in patients with absolute blood eosinophil counts  $\geq 300/\mu\text{L}$ . In the pivotal studies (Bleecker et al 2016, FitzGerald et al), compared with placebo, benralizumab 30 mg administered subcutaneously (benralizumab 30 mg every 4 weeks for the first 3 doses and then every 8 weeks thereafter) significantly reduced the annual asthma exacerbation rate, improved asthma symptom and lung function (pre-bronchodilator FEV1). The purpose of this trial is to confirm the efficacy and safety of benralizumab administration in asthma patients who are otherwise uncontrolled on current standard of care therapy. The question of the baseline blood eosinophil level that predictably ensures the clinical benefit in patients will also be addressed in the study by inclusion of patients with blood eosinophil counts  $\geq 300/\mu\text{L}$  and  $< 300/\mu\text{L}$ .

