## **1.2 Rationale for study design, doses and control groups**

This is a regional study designed to investigate the safety and efficacy of the fixed dose benralizumab (30 mg) administered subcutaneously (SC) every 4 weeks for the first 3 doses and then every 8 weeks thereafter in exacerbation-prone asthma patients who remain uncontrolled on medium to high-doses ICS-LABA with or without oral corticosteroids and other asthma controller(s).

Primary efficacy will be determined based on reduction in the rate of asthma exacerbations over 48 weeks for benralizumab versus placebo. In order to avoid biasing the results, the study will be randomised and double-blinded with stratification by age group (adult or adolescent), country/region and eosinophil category ( $\geq 300/\mu\text{L}/< 300/\mu\text{L}$ ).

The study will randomise patients with screening blood eosinophils  $\geq 300/\mu\text{L}$  and  $< 300/\mu\text{L}$  at a ratio of about 2:1. The 2:1 stratification of patients with eosinophil counts  $\geq 300/\mu\text{L}$  and  $< 300/\mu\text{L}$  is intended as a means of enriching the population for patients most likely to respond to benralizumab (ie,  $\geq 300/\mu\text{L}$ ), while still accommodating patients below this threshold in order to help understand where additional benefit drops off.

The benralizumab dose (30 mg SC, fixed) and the maintenance regimens are based on all available safety, efficacy and immunogenicity data, as well as population exposure-response modeling, and stochastic trial simulations from earlier phase benralizumab trials. In particular, Phase 2b MI-CP220 study (Castro et al 2014) showed that fixed doses of

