### 1.3 Benefit/risk and ethical assessment

There are few treatment options for patients whose asthma remains uncontrolled on medium to high-dose ICS-LABA (GINA 2014). The evidence base for oral add-on therapies (ie, oral corticosteroids, leukotriene inhibitors, and xanthenes) is extremely limited. Anti-IgE therapy (ie, omalizumab) may improve control in patients with severe asthma and IgE-mediated allergy to a perennial allergen. Tiotropium is a long-acting bronchodilator that has recently been shown to produce improvement in lung function and exacerbation risk (pooled data) in patients with severe asthma, with inconsistent effects on other measures of asthma control (Kerstjens et al 2012). As such, new therapies are needed for asthma management in patients who remain uncontrolled on standard of care.

In adult patients whose asthma was poorly controlled on medium-to-high dose ICS-LABA benralizumab, at fixed doses of  $\geq 20$  mg, produced improvements in multiple metrics of asthma control including the annual rate of asthma exacerbations, lung function, ACQ-6 scores, and symptoms (Castro et al 2014). These findings have subsequently been confirmed in two large Phase 3 studies (Bleecker et al 2016, FitzGerald et al) where a fixed dose of 30 mg was given either every 4 weeks or every 8 weeks. Clinical benefit appeared to be greatest in patients with blood eosinophil counts  $\geq 300/\mu\text{L}$ . The blood eosinophil count below which

benralizumab is generally not effective remains unclear at this point in time, and will be explored in this study.

Development of anti-drug antibodies (ADA) to benralizumab has been documented. Theoretical risks of developing ADA include decreased drug efficacy and hypersensitivity reactions (e.g., anaphylaxis or immune complex disease). There was no apparent impact of ADA on overall benralizumab safety or efficacy in the previous Phase 3 studies in asthma. Serious hypersensitivity reactions (including anaphylaxis) are an identified risk of biologic therapy, including benralizumab. Anaphylaxis may be life-threatening. Risk minimization includes observation in line with clinical practice at the clinical site following IP administration for the appearance of any acute drug reactions.

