### 8.2 Sample size estimate

The study will randomise patients with baseline blood eosinophil counts  $\geq 300/\mu\text{L}$  and  $< 300/\mu\text{L}$  at a ratio of about 2:1. The 2:1 stratification ratio is intended as a means of enriching the population for patients most likely to respond to benralizumab (i.e.,  $\geq 300/\mu\text{L}$ ), while still including patients below this threshold in order to help understand efficacy and safety in this group. The study is powered for the primary efficacy analysis of the patients with baseline blood eosinophils  $\geq 300/\mu\text{L}$ .

The efficacy analyses will comprise both adults and adolescent patients.

For the primary endpoint annual asthma exacerbation rate, approximately 222 adults and adolescent patients with baseline blood eosinophil counts  $\geq 300/\mu\text{L}$  per treatment arm (approximately 444 in total) will need to be randomised to achieve approximately 90% power

CCI

As stated

previously an about 2:1 ratio will be used for patients with baseline blood eosinophil counts  $\geq 300/\mu\text{L}$  and  $< 300/\mu\text{L}$ . Therefore the study will also randomise approximately 111 patients/arm (approximately 222 in total) with baseline blood eosinophil counts  $< 300/\mu\text{L}$ . The  $< 300/\mu\text{L}$  stratum will be closed for all patients, when a total of 222 adults and adolescent patients have been randomised in the stratum. So a total of approximately 666 adult and adolescent patients are expected to be randomised in the study. Among these 666 patients, at least 70% patients will be randomised from China.

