### **8.5.1 Analysis of the primary variable (s)**

The primary efficacy variable is the annual asthma exacerbation rate and the primary analysis is to compare the annual asthma exacerbation rate of benralizumab group with placebo group in patients with baseline blood eosinophil counts  $\geq 300/\mu\text{L}$ .

The null hypothesis is that the exacerbation rate on benralizumab is equal to the exacerbation rate on placebo. The alternative hypothesis is that the exacerbation rate on benralizumab is not equal to the exacerbation rate on placebo, ie,

*H0: Rate ratio (benralizumab vs. Placebo) = 1*

*Ha: Rate ratio (benralizumab vs. Placebo)  $\neq 1$*

Exacerbation rate in the benralizumab group will be compared to exacerbation rate in the placebo group using a negative binomial model. The response variable in the model will be the number of asthma exacerbations over the 48-week treatment period. The model will include covariates of treatment group, region (China/non-China), number of exacerbations in the year before the study, and the use of maintenance oral corticosteroids (yes/no). The logarithm of the follow-up time will be used as an offset variable in the model.

The estimated treatment effect (i.e., the rate ratio of benralizumab versus placebo), corresponding 95% confidence interval (CI), and two-sided p-value for the rate ratio will be presented. In addition, the exacerbation rate and the corresponding 95% CI within each treatment group will be presented.

In addition, the exacerbation rate will also be summarized in patients with baseline blood eosinophil counts  $< 300/\mu\text{L}$ ,  $< 150/\mu\text{L}$ ,  $150\text{-}299/\mu\text{L}$ ,  $300\text{-}449/\mu\text{L}$  and  $\geq 450/\mu\text{L}$  separately.

The individual exacerbation criteria (ER visit due to asthma that required systemic corticosteroids, hospitalization due to asthma, or use of systemic corticosteroids) will also be summarized.

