### **8.5.2 Analysis of the secondary variable(s)**

#### **8.5.2.1 Analysis methods for secondary efficacy variables**

Key secondary efficacy endpoints in this study are:

- Change from baseline in pre-bronchodilator FEV1 at Week 48
- Change from baseline in asthma symptom total score at Week 48

Other secondary efficacy endpoints include

- Proportion of patients with  $\geq 1$  asthma exacerbation
- Time to the first asthma exacerbation

- Annual rate of asthma exacerbations that are associated with an emergency room/urgent care visit or a hospitalization
- Change from baseline in total rescue medication use (average puffs/day)
- Change from baseline in morning and evening PEF at Week 48
- Change from baseline in asthma symptom day time/night time scores at Week 48
- Change from baseline in number of nights with awakening due to asthma and requiring rescue medication
- ACQ-6
- SGRQ

All the secondary efficacy endpoints will be analysed in patients with baseline blood eosinophil counts  $\geq 300/\mu\text{L}$ . In addition, the 2 key secondary efficacy endpoints will be analysed in patients with baseline blood eosinophil counts  $< 150/\mu\text{L}$ ,  $< 300/\mu\text{L}$ ,  $150\text{-}299/\mu\text{L}$ ,  $300\text{-}449/\mu\text{L}$  and  $\geq 450/\mu\text{L}$  separately.

Change from baseline in pre-bronchodilator FEV1 at Week 48 will be compared between the benralizumab group and placebo using a repeated measures analysis on patients with a baseline pre-bronchodilator FEV1 and at least 1 post-randomisation pre-bronchodilator FEV1 in the full analysis set. The dependent variable will be the change from baseline in pre-bronchodilator FEV1 at post-baseline protocol-specified visits (up to the EOT Visit). Treatment group will be fitted as the explanatory variable, and region (China/non-China), baseline pre-bronchodilator FEV1, visit, the interaction term of visit and treatment, and the use of maintenance oral corticosteroids (yes/no) will be fitted as covariates. Visit will be fitted as a categorical variable, and the variance-covariance matrix will be assumed to be unstructured. If the procedure does not converge then a compound symmetric variance-covariance matrix will be used instead. The model is:

*Change in FEV1 = Treatment group + baseline FEV1 + region + maintenance oral corticosteroids + visit + treatment \* visit*

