### **8.5.3 Subgroup analysis**

To explore the uniformity of the detected overall treatment effect on the primary efficacy variable, subgroup analyses and statistical modeling including testing for interaction between treatment and covariates will be performed in patients with baseline blood eosinophil counts  $\geq 300/\mu\text{L}$  for the following factors: Oral corticosteroids (OCS) use at baseline (yes, no), gender, age (<18, 18 - <65, and  $\geq 65$  years), region (China/non-China), country, BMI ( $\leq 35$ ,  $> 35$   $\text{kg}/\text{m}^2$ ), the number of exacerbations during the previous year (2,  $\geq 3$  exacerbations), the number of exacerbations during medium-high ICS/LABA treatment prior to study enrolment (2,  $\geq 3$  exacerbations), ICS dose at study enrolment (medium, high) and nasal polyps (yes, no). Data will be analysed by negative binomial regression similar to the primary analysis and the same output will be presented for each subgroup as for the primary analysis. For the

statistical modeling including interaction effects, the estimate of the interaction effects will be presented together with the corresponding p-value. These analyses are to be considered as exploratory and will be performed on the full analysis set.

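### The protocol says it will explore the eosinophil level at which benefit holds, but specifies only separate results by band and no treatment-by-eosinophil analysis across the range

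*Supplement*

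**What the plan says.** Three places in the rationale raise the question of how benefit depends on eosinophils. Section 1.1.2: "The question of the baseline blood eosinophil level that predictably ensures the clinical benefit in patients will also be addressed in the study", by enrolling on both sides of 300/µL. Section 1.2 gives the reason for enrolling below 300/µL as "accommodating patients below this threshold in order to help understand where additional benefit drops off". Section 1.3 says that the count below which "benralizumab is generally not effective remains unclear at this point in time, and will be explored in this study".

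The analysis sections provide the following.

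- **Primary endpoint (Section 8.5.1).** The primary comparison is in patients at or above 300/µL. "The model will include covariates of treatment group, region (China/non-China), number of exacerbations in the year before the study" and maintenance oral corticosteroid use; there is no eosinophil term. Then: "In addition, the exacerbation rate will also be summarized in patients with baseline blood eosinophil counts" <300, <150, 150-299, 300-449 and ≥450/µL, each separately.
- **Key secondary endpoints (Section 8.5.2.1).** "In addition, the 2 key secondary efficacy endpoints will be analysed in patients with baseline blood eosinophil counts" in the same five bands, again separately.
- **Interaction testing (Section 8.5.3).** "subgroup analyses and statistical modeling including testing for interaction between treatment and covariates will be performed in patients with baseline blood eosinophil counts" of 300/µL or more. The ten factors listed are oral corticosteroid use, gender, age, region, country, BMI, two exacerbation-history counts, ICS dose and nasal polyps. Eosinophil count is not one of them.
- **Sample size (Section 8.2).** About 222 "per treatment arm (approximately 444 in total) will need to be randomised to achieve approximately 90% power" in the ≥300 stratum, and about 111 per arm (222 in total) below 300/µL with no power stated.

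**The concern.** The question in the rationale is about a difference: how the effect of benralizumab changes as the eosinophil count falls. The protocol gives a set of separate results, and the one section that tests interactions leaves out both the patients below 300/µL and the variable of interest.

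Separate results do not estimate a change in effect. A significant rate ratio at or above 300/µL beside a non-significant one in a smaller band is easily taken as evidence of a threshold, and a wide interval in a narrow band is easily taken as evidence of no effect. The five bands also overlap, since <300 is the union of <150 and 150-299, so they are not five independent pieces of evidence. At stake is how much the lower-eosinophil third of the trial tells a reader about where benefit drops off. The alpha-controlled results are not affected.

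**Working it through.** **Inputs.** 222 and 111 per arm (Section 8.2); 1:1 allocation (Section 3.3); 48 weeks, t = 0.92 year (Section 8.4.1.1); two-sided 5%. The assumed rate ratio and dispersion are redacted. The placebo rate r0 = 0.88 per patient-year appears only in the amendment history (Appendix H, Version 4.0), so it is used here as an assumption. Dispersion k is varied from 0.4 to 1.5. The documents give no eosinophil distribution, so a band of 55 per arm (an equal split of the <300 stratum into <150 and 150-299) is also an assumption.

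**The plan's own figures.** 444 + 222 = 666 and 444/222 = 2, as stated. The 222 per arm cannot be reproduced uniquely without the redacted values, but it is plausible: rate ratio 0.65 with k = 0.4 needs 223 per arm, and 0.60 with k = 1.0 needs 214. The design is therefore calibrated: for each k, find the rate ratio RR that gives 90% power at 222 per arm.

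**Formulas.**

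- Var(log RR) = [(1/(t·r0) + k) + (1/(t·r0·RR) + k)] / n per arm
- Power = Φ(|log RR|/SE − 1.96)
- Interaction: the variance is the sum of the two strata's variances

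**Worked case, k = 1.0, t = 0.92.** 1/(t·r0) = 1.235. The calibrated RR is 0.607, |log RR| = 0.499. The bracket is 2.235 + 3.035 = 5.270.

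- 222 per arm: SE = √(5.270/222) = 0.154; power Φ(3.24 − 1.96) = 90%.
- 111 per arm, same RR: SE = √(5.270/111) = 0.218; power Φ(2.29 − 1.96) = 63%.
- 55 per arm, same RR: SE = √(5.270/55) = 0.310; power Φ(1.61 − 1.96) = 36%.
- Interval if the true RR is 1 (bracket 4.471): multiply and divide by exp(1.96 × 0.201) = 1.48 at 111 per arm, and by exp(1.96 × 0.285) = 1.75 at 55 per arm.
- Binary interaction, <300 effect nil: SE = √(0.0237 + 0.0403) = 0.253; power Φ(0.499/0.253 − 1.96) ≈ 51%.
- Binary interaction, <300 effect half on the log scale: SE = √(0.0237 + 0.0434) = 0.259; power Φ(0.250/0.259 − 1.96) ≈ 16%.

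**Range at t = 0.92.**

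| k | Calibrated RR | Power at 111 / 55 per arm | CI factor at RR 1, 111 / 55 per arm | Interaction power, <300 nil / half | Ratio of rate ratios detectable at 80% power |
|---|---|---|---|---|---|
| 0.4 | 0.649 | 63% / 36% | 1.40 / 1.61 | 51% / 16% | 0.54 |
| 1.0 | 0.607 | 63% / 36% | 1.48 / 1.75 | 51% / 16% | 0.49 |
| 1.5 | 0.577 | 63% / 36% | 1.55 / 1.86 | 50% / 16% | 0.46 |

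Using t = 1 year changes little: interaction power 50-51%, CI factors 1.39-1.53 at 111 per arm and 1.59-1.83 at 55 per arm.

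**Reading.** With a true RR of 1, an interval centred there from the whole <300 stratum has a lower limit of 0.71, 0.68 and 0.65 for the three values of k, each above the calibrated RR. It would separate no effect from the design effect. At 55 per arm the lower limits are 0.62, 0.57 and 0.54, each below the calibrated RR, so such a band would not. What a continuous-eosinophil model gains over the bands cannot be computed without the eosinophil distribution.

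**The case against.** The strongest reply is that the SAP is not shown. Section 8.1 announces one, and Sections 8.5, 8.5.2.2 and 8.5.4 leave further analyses or detail to it. An exploratory eosinophil-response model is ordinary SAP content. This stands to the extent that absence can be asserted only for the protocol. But Section 8.5.3 is not silent: it fixes the population and the factor list for interaction testing without deferring to the SAP, and its choice omits this comparison.

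Second, locating the drop-off is not among the objectives in Section 2. It is rationale, mostly in soft terms, and Section 8.2 describes the purpose of the <300 stratum as understanding efficacy and safety in that group. This also stands, and it is why the remedy should be exploratory.

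Third, limiting Section 8.5.3 to ≥300/µL is coherent for its own aim, which is uniformity of the primary effect in the primary population. That is true, but no other section takes up the eosinophil question.

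Fourth, the remedy has modest power, and a non-significant interaction could be misread as no difference. That is a reason to report estimates and intervals instead of a p-value, not a reason to leave the comparison out.

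**Conclusion.** The point holds for the protocol text: no specified analysis estimates how the treatment effect changes with eosinophils or contrasts it across 300/µL, although the rationale says this will be addressed or explored. It is worth correcting, but the primary and gatekept analyses are untouched.

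Two stronger readings are tempting. A reader might infer that the trial cannot answer its eosinophil question at all. The documents do not support that: the aim is exploratory, and under the assumptions above the whole <300 stratum gives a usefully narrow interval. A reader might also infer that the plan does nothing but summarise the bands. Section 8.5.2.1 says the two key secondary endpoints are analysed by band. The synopsis uses the weaker verb for those same endpoints, so the wording in Section 8.5.1 does not prove that no rate ratio or interval will be given for exacerbations.

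The 63%, 36% and 50% figures barely depend on the redacted rate ratio and dispersion once 90% power at 222 per arm is taken as given. The interval widths depend on the 0.88 placebo rate and on k, and anything said about the narrower bands depends on an assumed band size.

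**What to change.** In Section 8.5.3, add an exploratory analysis in all full-analysis-set patients, outside the gatekeeping family of Section 8.5:

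- Fit the primary negative binomial model plus baseline log eosinophil count (linear, or a spline with few knots fixed in advance) and its interaction with treatment. Report the rate ratio with 95% CI across the range, for example at 150, 300 and 450/µL.
- Report the treatment-by-stratum contrast (<300 versus ≥300/µL) as a ratio of rate ratios with 95% CI.
- Do the same for change in pre-bronchodilator FEV1 at Week 48, using its repeated-measures model.
- State that interpretation rests on estimates and intervals, and that neither a significant/non-significant pair of bands nor a non-significant interaction test will be read as showing or excluding a threshold.

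If the SAP already contains such an analysis, a cross-reference is enough.

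The cost is one extra exploratory model per endpoint, with limited power. It needs no new data, since the count is measured and randomisation is already stratified at 300/µL, and it uses no alpha. The band results can stay as they are.

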#### **8.5.4 Sensitivity analysis**

Sensitivity analyses for the primary endpoint and the key secondary endpoints based on different missing data mechanism assumptions including those expected to be more conservative such as missing not at random will be used to explore the robustness of any treatment effect, including multiple imputation approaches. Full details of the sensitivity analyses will be pre-specified in SAP and documented prior to database lock of the study.

#### **8.5.5 Interim analysis**

There is no interim analysis planned for this study. The study will remain blinded until database lock.

### **8.6 Independent adjudication committee for major adverse cardiac events and malignancies**

An independent adjudication committee will be constituted to provide an independent, external, systematic, and unbiased assessment of blinded data to confirm the diagnosis of: 1) Investigator-reported non-fatal myocardial infarction, unstable angina, non-fatal stroke (hemorrhagic, ischemic, embolic), as well as all deaths and 2) Investigator-reported malignancies during the study. The committee will operate in accordance with an Adjudication Committee Charter/Manual of Operations, which will also provide detail on specific information to enable a more robust review through adjudication process.

## **9. STUDY AND DATA MANAGEMENT BY ASTRAZENECA**

### **9.1 Training of study site personnel**

Before the first patient is entered into the study, an AstraZeneca representative will review and discuss the requirements of the Clinical Study Protocol and related documents with the investigational staff and also train them in any study specific procedures and WBDC, IWRS/IVRS, ePROs, and other systems to be utilised.

The Principal Investigator will ensure that appropriate training relevant to the study is given to all of these staff, and that any new information relevant to the performance of this study is forwarded to the staff involved.

The Principal Investigator will maintain a record of all individuals involved in the study (medical, nursing and other staff).

